#### **1.4 Research Questions**

KC has gained acceptance as a chosen and effective technique for the quality care of premature infants. However, it is still a new phenomenon in the NICU in Malaysia; also no data has been published regarding the effectiveness of KC in relation to the perception, knowledge and, practices of nurses. In addition, emotional stress also occurs among those mothers whose preterm infants have been admitted to the NICU. This study also explores the outcomes of mothers in terms of their perception, knowledge, barriers and level of stress regarding KC implementation as well as the outcomes for their premature infants; weight gain, LOS and breastfeeding rates associated with compliance with the practice of KC in a Malaysian setting. In view of the lack of literature on a locally contextualized education model for the teaching of kangaroo care, I questioned the need for drafting such an education programme. The main research question of this thesis is;

Can a locally contextualised kangaroo care education programme aimed towards both mothers and NICU nurses be effectively implemented?

To answer the above research question, the following were analysed.

1. Are there any statistically significant changes in mothers' perception, knowledge, perceived barriers regarding KC and their level of stress after participation in a KC-EP between control and experimental groups of mothers at pre-intervention (T0), 1-month post-intervention (T1) and 3-months post-intervention (T2)?
2. Does KC improve premature infants' weight gain, LOS, and breastfeeding rates between a control and an experimental group at pre-intervention (T0), 1-month post-intervention (T1) and 3-months post-intervention (T2)?
3. Are there any statistically significant changes in the nurses' perception, knowledge and practice of KC before and after participation in a KC-EP?

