The KC-EP's design for mothers was based on the above discussion and consisted of two (2) sessions (first meeting and subsequent meeting), ten (10) short messages and reminder updates, and three (3) telephone follow-ups, and the program started immediately within 24 to 48 hours of admission. The sessions included an overview or welcoming meeting with the mother during the admission of her premature baby to the NICU (10 to 15 minutes), followed by two more meetings (first 60-minute meeting and subsequent 15 to 20-minute meeting).

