### **3.14.5 Telephone call and short message via WhatsApp.**

To ensure continuity of the KC technique and quality of premature infant care, the researchers performed a follow-up through WhatsApp, sending a short message to the mother. This was a reminder about providing updates on the premature infant's performance of KC, the condition of the premature infant; i.e. body weight of preterm infant on discharge, at 1 month and 3 months corrected age, breastfeeding status every 2 weeks post-admission until 40 weeks post-admission. In addition, this continued every 4 weeks at 44 weeks, 48 weeks and 52 weeks of premature infant age [Table 3.2(a) & (b)]. The researchers also made three (3) telephone calls via WhatsApp during the program of which the first call was at 40 weeks post-admission, the second call was at 44 weeks (1 month) post-admission and the last call was at 52 weeks (3 months) post-admission. The purpose of the call was to find out if the mother had any doubts or had any problems linked to the objectives of the study at home and to advise the mother to contact the researcher at any time if she had any problems with KC and her premature infant's condition. All of the conversations were conducted using a very careful approach to ensure that the mothers were openly sharing their feelings and their appreciation of KC.

The program aimed to educate mothers on how to carry out KC and reduce their stress levels and how to strengthen their ability to breastfeed their premature infants. The nurses' workload in the NICU is generally very high, and nurses do not have enough time to assist

the mothers. Therefore, the entire program was allocated only 1 hour and 30 minutes. The experimental group had four sessions prepared and designed for the mothers, the specifics are set out in Appendix L and M. The program was administered in one session with between two (2) or four (4) mothers per group and one or two nurses involved at the first meeting. This was to ensure the nurses and mothers were given the same information , skills and shared attitudes.

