**Table 3.2(a): Schedule for Intervention and Instrument (KC-EP) for the Mothers' in Control and Experimental Groups**

Days/ Weeks	Control Group		Experimental Group		Person in charge
	Activities	Instrument	Activities	Instrument	
Admission Day	Routine NICU practice	Brief NICU orientation	Review (Medical Report)	Brief NICU orientation	Review (Medical Report)
Day 1 (PI: Week 28)					
Day 2		Breastfeeding Support, Hand Washing	KCQ (QI) & PSS: NICU:P&R KCPR Booklet	Simple ward orientation, First meeting	KCQs (QI) & PSS: NICU:P&R KCPR Booklet
Day 3		Breastfeeding Support + Attending mother whenever are approach by mother ad hoc		Short Message: WhatsApp (1)	Researcher
Day 4				Subsequent Meeting	Researcher
Day 5					
Day 6					
Day 7 (PI: Weeks 29)				Short Message: WhatsApp (2)	Researcher
Day 8					
Day 9					
Day 10 - Day 13					
Day 14 (PI: Week 30)				Short Message: WhatsApp (3)	Researcher

PI=Premature Infant; NICU=Neonatal Intensive Care Unit; KCRP Booklet=Kangaroo Care Progress Record Booklet;

**Table 3.2(b): Schedule for Intervention and Instrument (KC-EP) for the Mothers' in Control and Experimental Groups (Continued)**

Days/ Weeks/ Months	Control Group		Experimental Group		Person in charge
	Activities	Instrument	Activities	Instrument	
PI: Week 32	Routine NICU practice	Breastfeeding Support + Attending mother whenever are approach by mother ad hoc	Short Message: WhatsApp (4)		Researcher
PI: Week 34			Short Message: WhatsApp (5)		Researcher
PI: Week 36			Short Message: WhatsApp (6)		Researcher
PI: Week 38			Short Message: WhatsApp (7)		Researcher
PI: Week 40			Telephone Follow- up (1)		Researcher
PI: Week 44 (1st month)		KCQs & PSS: NICU:P&R (QI)	Short Message: WhatsApp (8)	KCQs & PSS: NICU:P&R (QI)	Researcher
PI: Week 48 (2nd months)			Telephone Follow- up (2)		
PI: Week 52 (3rd months)		KCQs & PSS: NICU:P&R (QI)	Short Message: WhatsApp (9)	KCQs & PSS: NICU:P&R (QI)	Researcher
			Telephone Follow- up (3)		

*PI= Premature Infant; NICU=Neonatal Intensive Care Unit; KCQ=Kangaroo care questionnaire; PSS: NICU=Parental Stress Scale: Neonatal Intensive Care Unit.*

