### **3.16.3 Mothers' Outcome Variables**

Quantitative data on mothers' data were obtained in Phase I and Phase III. The outcome variables were perception, knowledge, perceived barriers in relation to KC, and stress related to admission of preterm infant to the NICU. These variables were assessed three times from T0, T1 to T2. The mothers were instructed to complete Questionnaire I within 10 to 15 minutes without any reference to resources. Firstly, Questionnaire I was delivered at T0; before the KC-EP for mothers started. Next, the mothers were instructed to answer the same structured set of questions in Questionnaire I at T1 and T2 for the post-intervention data. Monitoring the level of personal belief regarding KC at T0, T1 and T2, helps mothers to maintain compliance with KC until their premature infant is 3 months old corrected age. KC, together with breastfeeding, may continue until the infant is 6 months old and breastfeeding combined with solid foods until the infant is 2 years old.

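### T1 and T2 are labelled 1 and 3 months post-intervention, but programme contact with experimental mothers runs through week 52, so they measure KC-EP with continuing contact, not an effect after it ended

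*Combined protocol and SAP*

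**What the plan says.** Section 1.4 calls T1 one month and T2 "3-months post-intervention". Section 3.16.3 has mothers repeat Questionnaire I at both times "for the post-intervention data".

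Section 3.13 builds the mothers' KC-EP from two sessions plus "ten (10) short messages and reminder updates, and three (3) telephone follow-ups". Section 3.14.5 also puts the calls inside the programme: "The researchers also made three (3) telephone calls via WhatsApp during the program". The first is at week 40, and "the second call was at 44 weeks (1 month) post-admission and the last call was at 52 weeks (3 months) post-admission". Messages go out every two weeks up to week 40, after which "this continued every 4 weeks at 44 weeks, 48 weeks and 52 weeks of premature infant age".

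Table 3.2(b) lists Questionnaire I at weeks 44 and 52 in both groups. In the experimental column those rows also hold messages 8 and 9, with the third call printed under week 52. The control column shows routine practice with no message or call, and section 3.18 says the researcher gave control mothers no KC input. No section says whether the form or the contact comes first within the week.

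The anchor for T1 and T2 varies. Section 1.4 uses the intervention. Section 3.13 and Table 3.2 use infant age. Section 3.18 uses NICU discharge. Section 3.14.5 describes weeks 44 and 52 as counted from admission.

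**The concern.** Research question 1 rests on four self-reported scores: perception, knowledge, perceived barriers and stress. If results are reported under the section 1.4 label, a reader will take a group difference at T2 as something still present three months after the programme stopped. On the plan's own schedule the programme has not stopped at T1 and has its last contacts in the week of T2.

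The contact is also one-sided. Section 3.14.5 says the calls look for doubts or problems tied to the study's objectives. Section 3.16.4 says KC information was shared in a WhatsApp group of experimental mothers to keep them practising. If such contact comes shortly before the form, it could influence answers in that group only.

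**Working it through.** The check is date arithmetic on the schedule, trying each possible zero point. The plan's figure to reproduce is 1 month (about 4.35 weeks) for T1 and 3 months (about 13.0 weeks) for T2 after the intervention.

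**Inputs**
- T1 at week 44 and T2 at week 52 of infant age (section 3.13 for T1; Table 3.2(b) for both).
- Calls at weeks 40, 44 and 52, and late messages at 44, 48 and 52 (section 3.14.5).
- As printed in Table 3.2(b): message 8 at week 44, call 2 at week 48, message 9 and call 3 at week 52.
- First meeting within 48 hours of admission, taken as day 2, or 1/7 week after day 1 (section 3.14.2; Table 3.2(a)).
- Corrected age at recruitment 28 to 36+6 weeks (section 3.7.1), treated here as age at admission.

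**1. From the latest scheduled contact**
- T1: 44 - 44 = 0 weeks. T2: 52 - 52 = 0 weeks. Text and table agree on this.
- If the form came first in its week, the previous contact is week 40 for T1 (44 - 40 = 4 weeks) and week 48 for T2 (52 - 48 = 4 weeks). At T1 further contacts are still to come; at T2 that week's contact is.

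**2. From the first teaching meeting**
- T1: 44 - 28 - 0.14 = 15.9 weeks for the youngest infants, and 44 - 36.86 - 0.14 = 7.0 weeks for the oldest.
- T2: 52 - 28 - 0.14 = 23.9 weeks and 52 - 36.86 - 0.14 = 15.0 weeks.
- Counting from the day-4 meeting (section 3.14.4) shortens each by two days.

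**3. From term (40 weeks)**
- T1: 44 - 40 = 4 weeks. T2: 52 - 40 = 12 weeks.
- Of the counts at fixed weeks 44 and 52, only this one gives roughly 1 and 3 months. It is corrected age, not time since the intervention.

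**4. From admission, read literally**
- An infant admitted at 28 weeks would be at 28 + 44 = 72 weeks when section 3.14.5 says 1 month. The admission wording cannot be meant literally.

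**5. From NICU discharge (section 3.18)**
- T1 falls before week 52, with contact still running, for any infant discharged before 52 - 4.35 = 47.65 weeks.
- T2 falls after week 52 only for infants discharged later than 52 - 13 = 39 weeks.

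The stated figure is therefore not reproduced from any intervention anchor.

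**Contact counts.** Section 3.13 gives 10 + 3 = 13 contacts beyond the sessions; Table 3.2 shows 9 + 3 = 12. In weeks 44 to 52, section 3.14.5 gives 3 messages and 2 calls (5), and the table as printed gives 2 and 2 (4). The third call sits in a row with no week label, so the printed position of the second call may be a layout shift.

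**The case against.** The strongest reply is that the programme means the teaching sessions only. Section 3.14.5 allots the entire programme an hour and a half, section 3.16 describes the KC-EP as theory and practical sessions, section 3.16.2 places T1 and T2 after the structured programme, and Appendix L sets the posttests at the first and third month of it. On that reading both assessments do follow the programme. However, it conflicts with section 3.13 and with the statement that the calls were made during the programme, and step 2 shows it still does not give 1 and 3 months.

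Second, continuing contact is deliberate: mothers are meant to carry on KC until three months. That stands, and it is why a contrast with routine care remains meaningful. Hypothesis H1 and objective 1 make no explicit claim of persistence; the difficulty comes from the label.

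Third, section 3.14.5 describes the messages mainly as prompts for updates and the calls as check-ins inviting mothers to get in touch. Section 3.16.4 gives no dates for the KC information it mentions. No teaching is documented in week 44 or 52. This stands: a same-week prompt is possible, not shown.

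A reader might infer that the group differences are inflated by some known amount. The documents give no figure for such a shift, and the standard deviation in section 3.7.2 relates to infant weight gain, so it cannot scale the mothers' questionnaires.

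**Conclusion.** The timing label is wrong for what is measured. The gap from the latest scheduled contact is 0 weeks at both assessments, or about 4 weeks if the form is completed first. This takes weeks 44 and 52 as infant age and the messages and calls as programme components, as section 3.13 states; it does not depend on which week the second call fell in.

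T1 and T2 can describe KC-EP with continuing contact against routine care. They cannot show an effect 1 or 3 months after the programme ended, nor separate the teaching from contact around the form. A reader might go further and conclude that the scores show no valid programme effect. The documents do not support that: the schedule narrows the meaning of the contrast without making it empty. The size and direction of any prompt effect are unknown.

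**What to change.** - Choose one anchor. In sections 1.4, 3.16.3 and 3.18 and in Table 3.2, relabel T1 and T2 as 1 and 3 months corrected age (44 and 52 weeks), with programme contact continuing. Align the post-admission wording in section 3.14.5.
- State that Questionnaire I is answered and returned before that week's message or call. Section 3.16 reports data collection as complete, so where forms are already in hand, report the order, or that it is unknown, as a limitation.
- Make no claim of persistence after the programme.
- Reconcile the week of the second call (44 in section 3.14.5, 48 in the table as printed) and the number of messages (ten in section 3.13, nine in the table).

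The cost is a few sentences of wording, with no extra visit or participant. The conclusion becomes slightly narrower. Placing the form first removes only that week's contact; earlier contacts remain part of the estimated effect.

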**Table 3.2(a): Schedule for Intervention and Instrument (KC-EP) for the Mothers' in Control and Experimental Groups**

Days/ Weeks	Control Group		Experimental Group		Person in charge
	Activities	Instrument	Activities	Instrument	
Admission Day	Routine NICU practice	Brief NICU orientation	Review (Medical Report)	Brief NICU orientation	Review (Medical Report)
Day 1 (PI: Week 28)					
Day 2		Breastfeeding Support, Hand Washing	KCQ (QI) & PSS: NICU:P&R KCPR Booklet	Simple ward orientation, First meeting	KCQs (QI) & PSS: NICU:P&R KCPR Booklet
Day 3		Breastfeeding Support + Attending mother whenever are approach by mother ad hoc		Short Message: WhatsApp (1)	Researcher
Day 4				Subsequent Meeting	Researcher
Day 5					
Day 6					
Day 7 (PI: Weeks 29)				Short Message: WhatsApp (2)	Researcher
Day 8					
Day 9					
Day 10 - Day 13					
Day 14 (PI: Week 30)				Short Message: WhatsApp (3)	Researcher

PI=Premature Infant; NICU=Neonatal Intensive Care Unit; KCRP Booklet=Kangaroo Care Progress Record Booklet;

**Table 3.2(b): Schedule for Intervention and Instrument (KC-EP) for the Mothers' in Control and Experimental Groups (Continued)**

Days/ Weeks/ Months	Control Group		Experimental Group		Person in charge
	Activities	Instrument	Activities	Instrument	
PI: Week 32	Routine NICU practice	Breastfeeding Support + Attending mother whenever are approach by mother ad hoc	Short Message: WhatsApp (4)		Researcher
PI: Week 34			Short Message: WhatsApp (5)		Researcher
PI: Week 36			Short Message: WhatsApp (6)		Researcher
PI: Week 38			Short Message: WhatsApp (7)		Researcher
PI: Week 40			Telephone Follow- up (1)		Researcher
PI: Week 44 (1st month)		KCQs & PSS: NICU:P&R (QI)	Short Message: WhatsApp (8)	KCQs & PSS: NICU:P&R (QI)	Researcher
PI: Week 48 (2nd months)			Telephone Follow- up (2)		
PI: Week 52 (3rd months)		KCQs & PSS: NICU:P&R (QI)	Short Message: WhatsApp (9)	KCQs & PSS: NICU:P&R (QI)	Researcher
			Telephone Follow- up (3)		

*PI= Premature Infant; NICU=Neonatal Intensive Care Unit; KCQ=Kangaroo care questionnaire; PSS: NICU=Parental Stress Scale: Neonatal Intensive Care Unit.*

### **3.15 Nurses' Kangaroo Care Education Program (KC-EP)**

The KC-EP for nurses is a special program developed to assist nurses in sharing evidence about the benefits of KC that can be received by the mother of a preterm infant. Most of the available materials are generally used to address specific guidelines and practice protocols for NICU nurses to perform KC. Therefore, a special standardized content module in terms of KC's advantages for mother-infant dyads was formulated. The KC-EP focused on the psychological and physical aspects related to the preparation and implementation of the KC procedure (before, during, and after). On the other hand, the interpersonal communication or interaction between the nurses and the mothers in the NICU was developed for the psychological benefits and to foster good relationships between mothers and nurses. In other words, the KC-EP for nurses was more structured in terms of contextualization of the needs of Malaysia's regional culture. The positive point was that these prepared short notes, such as flipcharts and flyers in both languages, could be used as a quick reference for nurses to illustrate kangaroo care techniques to premature infant mothers. The general purpose of this program (KC-EP) was to ensure that the intervention with the mother-infant dyads was successful, and no cost was necessary. The practical goals were to:

- a. Provide nurses with educational information related to KC for the quality of premature infant care in the hospital and after returning home.
- b. Assist mothers during their premature infant's hospitalization in terms of situation and environment, facilities, and routine care in the NICU.
- c. Develop interpersonal communication and interaction between neonatal nurses and mothers.
- d. Support mothers with respect to psychological aspects following the birth of their premature infant.

e. Advocate for mothers to carry out at least 1 hour of KC per day and achieve 4 to 5 hours a week within the first 3 months.

**i) Contents Module Theory and Practical (8 hour)**

Module contents were organized to meet the objectives of this study. Purposes included the definition of KC, method of KC, benefits of KC, indication and contraindication of KC, guidelines and protocol for KC, recognized signs and symptoms of deterioration during and after the KC procedure, preparation of premature infant-mothers and equipment before, during and after the KC procedure, and showing how to record the infants' outcomes data for both groups in the KCPR booklet provided. The nurse should have been able to get a clear understanding of the programme and of the physiology and benefits of KC in detail and demonstrate the technique as well [Appendix P, Q(a)& Q(b)].

- 1) To define the term and amount of KC.
- 2) To explain the physiology and method of KC.
- 3) To state the benefits of KC to mother-infant dyads.
- 4) To state the indication and contraindication for kangaroo care and eligibility criteria for mothers and premature infants.
- 5) To state the guidelines and protocols before, during, and after the kangaroo care method.
- 6) To recognize signs and symptoms of deterioration among premature infants before, during , and after the method.
- 7) To state the preparation before, during and after the kangaroo care method
- 8) To list the equipment for kangaroo care method ;
  - 8.1 For infants
  - 8.2 For mothers
- 9) To educate and guide on recording in the KCPR booklet.
- 10) To demonstrate and return-demonstrate the KC method.

### **3.15.1 The process of delivery and how and who to conduct the KC-EP for nurses.**

Face-to-face or direct contact is the best adult teaching method for neonatal care since there is no existing research to determine if different delivery modes can produce better results (Aranda, 2008). The delivery method must evaluate the effectiveness of the intervention programme, the different methods used, and the magnitude of an intervention despite similar intervention material. Face-to-face or interpersonal communication was identified as the delivery method for KC-EP in this study after a literature review.

With the knowledge they have learned, nurses will be confidently active in advocating for the mother to carry out kangaroo care for their premature infants in the NICU, which can improve mother-infant dyad bonding, and reduce stress and anxiety among mothers (Liu et al., 2010). The above statement addresses the delivery method of KC-EP and the use of the empowerment concept (partnership, participation, and collaboration) in implementing KC-EP. The researchers distributed educational information and suggested that nurses should be aware of the kangaroo treatment method. The involvement and cooperation of nurses (first meeting and 7th day after intervention) and WhatsApp group discussions between nurses and researchers (face-to-face and one-to-one) were strengthened. Nurses were allowed to ask and discuss any questions or issues during meetings but to maintain the confidentiality of the conversations.

### **3.15.2 When, Where and How Much Will KC-EP be Delivered**

Bakermans-Kranenburg et al., (2003) also found that the psychological support received by non-professional interveners ( $d=0.42$ ) was greater than the professional interveners ( $d=20$ ). Professional intervener Bakermans-Kranenburg et al., (2003) refers to a trained clinical psychologist or counselor, whereas non-professional interveners refer to nurses performing many roles such as caregivers or supporters. This is likely because mothers meet more often

with nurses, and nurses can have a particular effect on the mother's care for her premature infant (Griffin, Wishba, Kavanaugh, 1988). Thus, nurses were the main interveners in this research.

On the basis of the above discussion, the program designed for the nurse's KC-EP consisted of two (2) sessions (first and posttest after the 7th day intervention program), one (1) short message reminder and an update. The program was started immediately after the pretest. The program included theory (4 hour) and practice (4 hour) during the nurses' shift in NICU.

